10.3.2.2.2 Analysis of Other Secondary Endpoints

The analysis of other secondary endpoints will be conducted for Treatment Cohort Period 1 only.

Absolute change from baseline in LCI_{5.0}

The analysis of LCI_{5.0} will be similar to those specified for the MMRM analysis of LCI_{2.5}, with the absolute change from previous study baseline in LCI_{5.0} at each visit as the dependent variable; and replacing the baseline LCI_{2.5} with baseline LCI_{5.0} of the previous studies as a continuous covariate. Figure for absolute change from previous study baseline in LCI_{5.0} will be plotted similar to absolute change in LCI_{2.5} above. Descriptive summary based on the current study baseline for P-L/I, similar to the summary of LCI_{2.5}, will be provided separately.

Absolute/relative change from baseline in ppFEV₁

The analysis of ppFEV₁ will be similar to those specified for the MMRM analysis of LCI_{2.5}, with the absolute or relative change from previous study baseline in ppFEV₁ at each visit as the dependent variable, respectively; and removing the continuous covariate baseline LCI_{2.5}. Figure for absolute change from previous study baseline in ppFEV₁ will be plotted similar to absolute change in LCI_{2.5} above. Descriptive summary based on the current study baseline for P-L/I, similar to the summary of LCI_{2.5}, will be provided separately.

Absolute change from baseline in body weight and weight-for-age-z-score

The analysis of body weight and weight-for-age z-score will be similar to the MMRM analysis described above for LCI_{2.5}, with the absolute change from previous study baseline in weight or weight-for-age z-score, respectively, at each visit as the dependent variable; and removing the continuous covariate baseline LCI_{2.5}. Figure for weight and weight-for-age Z-score will be plotted similar to absolute change in LCI_{2.5} above. Descriptive summary based on the current study baseline for P-L/I, similar to the summary of LCI_{2.5}, will be provided separately.

Absolute change from baseline in height and height-for-age-z-score

The analysis of height and height-for-age Z-score will be similar to those specified for the MMRM analysis of LCI_{2.5}, with the absolute change from previous study baseline in height or height-for-age z-score, respectively, at each visit as the dependent variable; and replacing the baseline LCI_{2.5} with baseline height or height-for-age z-score of the previous studies, respectively, as a continuous covariate. Figure for height and height-for-age Z-score will be

plotted similar to absolute change in LCI_{2.5} above. Descriptive summary based on the current study baseline for P-L/I, similar to the summary of LCI_{2.5}, will be provided separately.

Absolute change from baseline in TSQM domains

For TSQM domains, the analysis will be similar to those specified for the MMRM analysis of LCI_{2.5}, with the absolute change from previous study baseline in each domain at each visit as the dependent variable; and replacing the baseline LCI_{2.5} with domain baseline of the previous studies as a continuous covariate. Descriptive summary based on the current study baseline for P-L/I, similar to the summary of LCI_{2.5}, will be provided separately.

Number of pulmonary exacerbations (109 Subjects Only)

The number of pulmonary exacerbations will be analyzed using negative binomial regression model (PROC GENMOD) with two treatment groups: L200/I-L/I based on 109 FAS including events in the Cumulative Study Period, and P-L/I based on 109 ROS including events in the Current Study Period. All pulmonary exacerbation events in each corresponding Study Period will be included.

The model will include treatment (L200/I-L/I and P-L/I), weight (<25 kg and ≥25 kg) and ppFEV₁ severity at screening of the previous study (<90 versus ≥90). The log of time spent for each Study Period (end date of the Study Period – first dose date of the corresponding Study Period +1) in patient-years will be treated as the offset in this model.

The data during the placebo-controlled period for subjects randomized to the placebo group in Study 109 will be analyzed using a similar negative binomial regression model without the treatment in the model. Note the placebo rate might be slightly different from that estimated in Study 109 final CSR analyses, which included two arms (placebo and active) instead of the placebo arm only in this model.

The annualized (in 48 weeks) event rate of pulmonary exacerbation, defined as number of pulmonary exacerbations divided by total exposure in each study period, will be summarized and plotted using boxplot. In addition, number of events per patient-year with 95% CI from the model will be provided.

Time-to-first pulmonary exacerbation (109 Subjects Only)

Time-to-first pulmonary exacerbation will be analyzed and plotted using the estimates from Kaplan-Meier analysis (KM analysis) in two approaches:

- KM approach 1 includes two treatment groups: 1) L200/I-L/I based on 109 FAS including time-to-first event in the Cumulative Study Period; and 2) P-L/I based on 109 ROS including time-to-first event in the Current Study Period;
- KM approach 2 includes one treatment group, placebo, based on 109 FAS including time-to-first event in the Previous Study Period only.

Both on-treatment events and events after treatment discontinuation will be considered. For subjects enrolled in the Treatment Cohort Period 1 of Study 110, any subject without a pulmonary exacerbation before completion of the eligible analysis period will be considered censored at the end of the analysis period. For subjects not enrolled into the Study 110, any subject without a pulmonary exacerbation before withdrawal from Study 109 will be considered

censored at the time of withdrawal, and any subject who completes Study 109 without a pulmonary exacerbation will be considered censored at the last dose date in Study 109.

Event of having at least 1 pulmonary exacerbation (109 Subjects Only)

Number and percentage of subjects with at least one pulmonary exacerbation will be summarized for treatment groups: 1) L200/I-L/I based on 109 FAS including events in the Cumulative Study Period; and 2) P-L/I based on 109 ROS including events in the Current Study Period.

Number and percentage of subjects with at least one pulmonary exacerbation will also be summarized for Placebo based on 109 FAS including events in the Previous Study Period in a separate column.

Subjects who have no exacerbations through the end of the corresponding Study Period will be considered as having no event. A bar chart summarizing the percentage of subjects with at least one pulmonary exacerbation will be provided.

Rate of change in LCI_{2.5}, LCI_{5.0} (Subjects from LCI Set Only) and ppFEV₁

Linear mixed-effects (LMM) analyses will be conducted to estimate the overall rate of change in LCI_{2.5}, LCI_{5.0}, and ppFEV₁ during the Cumulative Study Period based on the LCI Set or 110 LCI Set for LCI measurements and FAS or 110 FAS for ppFEV₁.

For analysis of the rate of change in LCI_{2.5}, the dependent variable will be postbaseline value and the model will include treatment groups as the fixed effect (Placebo and L/I Overall), random intercept and slope for treatment duration (in patient years) and interaction of treatment groups and treatment duration. Model will adjust for previous study (Study 109 versus Study 011B), weight (<25 kg versus ≥25 kg) and ppFEV₁ severity (<90 versus ≥90), both as determined at screening in the previous study; and adjust for previous study baseline LCI_{2.5} as a continuous covariate. Rate of change in LCI_{5.0} will be analyzed similarly.

For analysis of the rate of change in ppFEV₁, the analysis will be similar to those specified for the LMM analysis of LCI_{2.5}, with the postbaseline value of ppFEV₁ as dependent variable; and removing the baseline LCI_{2.5} as the continuous covariate. For visits with both predose and postdose measurements, only predose measurements will be included.

In the LMM, measurements at and after Week 2 of Studies 109 or 011B for subjects randomized/enrolled in L200/I in Studies 109 or 011B, and measurements at and after Week 2 of Study 110 for subjects randomized in Placebo in Study 109, will be included to estimate the rate of change for L/I Overall; measurements at and after Week 2 up to Week 24 of Study 109 for subjects randomized in Placebo in Study 109 will be included to estimate the rate of change for Placebo. The rate of change will be reported as an annualized rate of change using patient years; 95% will also be provided.

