6.2 Secondary Endpoints

Treatment Cohort Period 1

The following efficacy endpoints are defined using baseline values in the previous study (i.e., Study 109 or Study 011B):

- Absolute change from baseline in LCI_{2.5} (subjects from Study 109 and Study 011B LCI Substudy only)
- Absolute change from baseline in sweat chloride
- Absolute change from baseline in body mass index (BMI)
- Absolute change from baseline in Cystic Fibrosis Questionnaire – Revised (CFQ-R) respiratory domain score

The following efficacy endpoints are defined using baseline values in the current study (i.e., Study 110):

- Absolute change from baseline in LCI_{2.5} (subjects from Study 109 and Study 011B LCI Substudy only)
- Absolute change from baseline in sweat chloride
- Absolute change from baseline in BMI
- Absolute change from baseline in CFQ-R respiratory domain score

Treatment Cohort Period 2

- Safety, as determined by AEs and serious adverse events (SAEs), liver function tests (LFTs), and ophthalmologic examinations

Observational Cohort

Safety, as determined by SAEs

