8.1 Efficacy Set

Full Analysis Set (FAS) includes all subjects who are randomized and dosed in Study 109, or subjects enrolled and dosed in Study 011B. The FAS treatment group assignment is shown in Table 8-1; the treatment group will be as randomized/enrolled in the previous studies.

Table 8-1 FAS Treatment Group Assignment in Study 110

Treatment Groups	Description
L200/I-L/I	Subjects randomized/enrolled to L200/I in the previous studies (Study 109 or Study 011B) ^a
P-L/I	Subjects randomized to placebo in Study 109 ^a

I: ivacaftor; L: lumacaftor; P: placebo.

^a Subjects who turn 12 years of age in the previous studies or Day 1 of this rollover study will begin receiving L400/I on Day 1. Subjects who turn 12 years of age after the Day 1 Visit of this rollover study will begin receiving L400/I at their next scheduled visit.

110 Full Analysis Set (110 FAS): The 110 FAS will include all subjects who rolled over from Study 109 and Study 011B, and who are enrolled and exposed to any amount of study drug in Study 110. The 110 FAS treatment group assignment is shown in Table 8-2; the treatment group will be as randomized/enrolled in the previous studies.

Table 8-2 110 FAS Treatment Group Assignment in Study 110

Treatment Groups	Description
L200/I-L/I	Subjects randomized/enrolled to L200/I in the previous studies (Study 109 or Study 011B) and enrolled and dosed in Study 110 ^a
P-L/I	Subjects randomized to placebo in Study 109 and enrolled and dosed in Study 110 ^a

I: ivacaftor; L: lumacaftor; P: placebo.

^a Subjects who turn 12 years of age in the previous studies or Day 1 of this rollover study will begin receiving L400/I on Day 1. Subjects who turn 12 years of age after the Day 1 Visit of this rollover study will begin receiving L400/I at their next scheduled visit.

109 Full Analysis Set (109 FAS): The 109 FAS will include all subjects who are randomized and exposed to any amount of study drug in Study 109.

109 Rollover Set (109 ROS): The 109 Rollover Set will include subjects who rolled over from Study 109 (enrolled in Study 110) and were exposed to any amount of study drug in Study 110.

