10.3.2.2 Analysis of Secondary Endpoints

10.3.2.2.1 Analysis of Secondary Endpoints

The analysis of secondary efficacy endpoints will be conducted for the Treatment Cohort Period 1 only.

Absolute change from baseline in LCI_{2.5}

The analysis for efficacy endpoints will be focused on within-group comparison and summaries. No between-groups comparisons will be performed.

For Treatment Cohort Period 1, the mixed model repeated measures (MMRM) analysis will be used for the Cumulative Study Period based on the FAS. It will include two treatment groups (L200/I-L/I and P-L/I) using baseline of the Previous Study Period.

The absolute change from previous study baseline (including all measurements at each visit, both on-treatment measurements and measurements after treatment discontinuation), will be included as the dependent variable; treatment group, visit, and treatment-by-visit interaction, as fixed effects; and subject as a random effect with adjustment for previous studies (Study 109 versus Study 011B), weight (<25 kg versus \geq 25 kg), and ppFEV₁ severity (<90 versus \geq 90), both as determined at screening in the previous studies, and previous study baseline LCI_{2.5} as a continuous variable.

In the model, visit will be treated as a class variable, and an unstructured covariance matrix will be assumed to model the within-subject variability. This model imposes no assumptions on the correlational structure and is considered robust. If there is a convergence problem due to the unstructured covariance matrix, the unstructured covariance matrix will be replaced by compound symmetry in the primary analysis. Denominator degrees of freedom for the *F*-test for fixed effects will be estimated using the Kenward-Roger approximation.¹ With a mixed-effects model as the primary analysis model based on restricted maximum likelihood estimation and assuming that conditional on fixed and random effects data are missing at random, no imputation of missing data will be done.

The result obtained from the model will be the treatment effect at each post baseline visit. The estimated mean within-group treatment effect, i.e., Least Square (LS) Means, SE, 95% CI, and a 2-sided within treatment group *P* value, will be provided. The LS means of absolute change from previous study baseline with 95% CI at each visit during the Cumulative Study Period will be plotted by treatment groups (L200/I-L/I and P-L/I).

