Raw values and absolute change from previous study baseline, at each visit during the Cumulative Study Period, will be summarized in a separate table. Descriptive statistics, including number of subjects (*n*), mean, SD, SE, median, minimum, and maximum, will be provided.

In addition, descriptive summary statistics will be provided in a separate table for raw values and absolute change from current study baseline for P-L/I for visits in the Current Study Period using 110 FAS, including number of subjects (*n*), mean, SD, SE, median, minimum, and maximum along with the 95% CI based on Normal approximation.

Absolute change from baseline in sweat chloride

The analysis of sweat chloride will be similar to the MMRM analysis described above for LCI_{2.5}, with the absolute change from previous study baseline in sweat chloride at each visit as the dependent variable; and replacing the baseline LCI_{2.5} with baseline sweat chloride of the previous studies as a continuous covariate. Figure for sweat chloride endpoints will be plotted similar to absolute change in LCI_{2.5} above. Descriptive summary based on the current study baseline for P-L/I, similar to the summary of LCI_{2.5}, will be provided separately.

Absolute change from baseline in BMI and BMI-for-age Z-score

The analysis of BMI and BMI-for-age Z-score will be similar to the MMRM analysis described above for LCI_{2.5}, with the absolute change from previous study baseline in BMI or BMI-for-age z-score, respectively, at each visit as the dependent variable; and removing the continuous

covariate baseline LCI_{2.5}. Figure for BMI and BMI-for-age z-score will be plotted similar to absolute change in LCI_{2.5} above. Descriptive summary based on the current study baseline for P-L/I, similar to the summary of LCI_{2.5}, will be provided separately.

Absolute change from baseline in CFQ-R respiratory domain

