The analysis of CFQ-R respiratory domain will be similar to those specified for the MMRM analysis of LCI_{2.5}, with the absolute change from previous study baseline in CFQ-R respiratory domain score at each visit as the dependent variable; and replacing the baseline LCI_{2.5} with baseline CFQ-R respiratory domain score of the previous studies as a continuous covariate. Figure for CFQ-R respiratory domain score will be plotted similar to absolute change in LCI_{2.5} above. Descriptive summary based on the current study baseline for P-L/I, similar to the summary of LCI_{2.5}, will be provided separately.

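### The MMRMs for BMI, weight, their z-scores and ppFEV1 carry no continuous baseline of their own, unlike every other continuous endpoint, and no reason is given

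*SAP*

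**What the plan says.** SAP 10.3.2.2.1 sets out the LCI2.5 model. Change from the previous-study baseline is regressed on treatment group, visit and their interaction. The model adjusts for previous study, screening weight (<25 or >=25 kg), screening ppFEV1 (<90 or >=90) and baseline LCI2.5 as a continuous variable. All other MMRMs are described as edits of this one.

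For one set of endpoints, baseline LCI2.5 is exchanged for the endpoint's own baseline. CFQ-R is modelled "with baseline CFQ-R respiratory domain score of the previous studies as a continuous covariate", and height "with baseline height or height-for-age z-score of the previous studies, respectively, as a continuous covariate". Sweat chloride, LCI5.0 and the TSQM domains follow the same rule.

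For the others it is only taken out:
- ppFEV1, absolute or relative change: "at each visit as the dependent variable, respectively; and removing the continuous covariate baseline" LCI2.5.
- BMI: the change "in BMI or BMI-for-age z-score, respectively, at each visit as the dependent variable; and removing the continuous" LCI2.5 covariate.
- Weight: the change in "weight or weight-for-age z-score, respectively, at each visit as the dependent variable; and removing the continuous covariate baseline" LCI2.5.

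On missing data the model section states that, "assuming that conditional on fixed and random effects data are missing at random, no imputation of missing data will be done". The analysis population is the FAS, which "includes all subjects who are randomized and dosed in Study 109, or subjects enrolled and dosed in Study 011B" (SAP 8.1), whether or not the child later enters Study 110.

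**The concern.** BMI is the only one of the four secondary efficacy variables in SAP 6.2 without its own baseline in the model. Of the three growth z-scores, only height-for-age has it. The visible text gives no reason (parts of the SAP are redacted).

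The per-visit LS means, confidence intervals and plots are the model-based results for these endpoints. Missing later visits are built into the FAS. Children who stopped study drug early cannot enter the Treatment Cohort (Protocol 8.1), and entry also depends on comorbidity, drug intolerance and compliance (Protocol 9.2). Such missingness may be related to baseline status. The missing-at-random assumption is conditional on what the model contains, so a change-score model without the baseline covers that route only in part. A continuous baseline would also usually reduce residual variance.

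**Working it through.** **1. The models side by side (SAP 10.3.2.2.1 and 10.3.2.2.2)**

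| Endpoint | Own continuous baseline | Retained screening stratum on the same quantity |
|---|---|---|
| LCI2.5, LCI5.0 | yes | none |
| Sweat chloride | yes | none |
| CFQ-R respiratory | yes | none |
| Height, height z-score | yes | none |
| TSQM domains | yes | none |
| Weight | no | weight, two levels |
| ppFEV1, absolute and relative | no | ppFEV1, two levels |
| BMI, BMI z-score, weight z-score | no | none; weight is an indirect proxy |

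**2. Inputs.** The documents give about 200 subjects from Study 109 and 56 from Study 011B, N = 256 (SAP 7.2). They give no SD, correlation, dropout rate or Study 109 allocation, and no figure on this point to reproduce. Assumed: baseline-change correlation r = -0.3 to -0.5; Study 109 split 100/100 or 67/133, so P-L/I has 100 or 67 subjects and L200/I-L/I has 156 or 189. With equal variances, r = -sqrt((1 - rho)/2), where rho is the baseline to follow-up correlation. So r = -0.5 is rho = 0.5, and r = -0.3 is rho = 0.82.

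**3. Precision.** Comparing model SEs without and with the baseline, and no strata, gives sqrt(2(1 - rho)/(1 - rho^2)): 1.155 at rho 0.5, 1.085 at 0.7, 1.026 at 0.9 and 1.013 at 0.95. This overstates the real gain, because the mean baseline is itself estimated. The true sampling variance of a group LS mean at the pooled mean baseline, in units of the variance of change, is (1 - r^2)/n + r^2/N, against 1/n unadjusted. For P-L/I with n = 100:
- r = -0.5: 0.75/100 + 0.25/256 = 0.00848 against 0.01000, so the SD is 7.9% lower.
- r = -0.3: 0.91/100 + 0.09/256 = 0.00945 against 0.01000, so the SD is 2.8% lower.

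The retained strata already take part of this. Simulated 256-subject trials with both strata in the model gave gains of 0.5-8.4% for BMI and the two z-scores, and 0.4-3.5% for weight and ppFEV1.

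**4. Missingness.** A single-visit simulation (1,000,000 subjects) kept each subject with probability 1/(1 + exp(-(1.4 + g x baseline))). The odds ratio is 1.65 per baseline SD at g = 0.5 and 2.72 at g = 1. Bias in mean change, in baseline SDs:

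| rho | g | Kept | No baseline | Two-level cut of baseline | Continuous baseline |
|---|---|---|---|---|---|
| 0.5 | 0.5 | 79.1% | -0.051 | -0.019 | -0.0006 |
| 0.5 | 1 | 76.3% | -0.100 | -0.037 | 0.0001 |
| 0.7 | 1 | 76.3% | -0.061 | -0.022 | 0.0001 |
| 0.9 | 1 | 76.4% | -0.020 | -0.007 | 0.0006 |

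The -0.100 has no stratum at all, which is not the SAP's model. A closer version is a three-visit unstructured MMRM with study and both strata (66,560 subjects, 15-30% of last-visit values missing, odds ratio 1.5-2.5 per baseline SD). Differences from the full-data fit, in SDs of change:
- Without baseline: 0.001-0.057, or 0.01-0.53 SE at n = 256 (95% CI coverage about 92-95%).
- Additive baseline: at most 0.006 if the baseline effect is constant over visits, but 0.007-0.050 if it grows.
- Baseline-by-visit: at most 0.006 in both cases.

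**5. Reported SE after adjustment.** The usual LS-mean SE treats observed baselines as fixed and leaves out r^2/N. At r = -0.5 with n = 156, reported over true SD is sqrt[(0.75/156)/(0.75/156 + 0.25/256)] = 0.91. With n = 189 it is 0.90. Simulated coverage of the population mean change for L200/I-L/I was 92-93%, against 94-95% without the baseline. For P-L/I it was 93-94%. At r = -0.3 the loss is 1 point or less.

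**The case against.** The strongest reply is that the split is not arbitrary. The endpoints without a continuous baseline are those tied to the weight and ppFEV1 strata, and those strata stay in the model. This stands as a likely explanation, though the SAP does not state it. It answers the concern only in part: a two-level cut left just over a third of the bias in step 4 even when it cut the baseline itself, and for BMI and the two z-scores the weight cut is only indirect.

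A reader might infer that the SAP departs from the protocol. It does not. Protocol 12.4.3 names a continuous baseline for LCI only, and leaves modelling of other continuous variables to the SAP. Nor does the SAP strip these endpoints of their own baseline: what it removes is baseline LCI2.5.

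Two technical objections also stand. An additive baseline may leave most of the bias (up to 0.050 against at most 0.057 SD), so the interaction belongs in the fix. And adjusted SEs are conditional on the observed baselines (step 5). That is a real cost if the target is the population mean change, and none if the target is conditional on those baselines. The SAP's other baseline-adjusted endpoints already carry it.

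A reader might also link this to the unstated study mix behind the LS means, since P-L/I contains only Study 109 subjects. That is a separate clarification for every MMRM. Any harm depends on a difference between studies that the documents do not give, and this point does not rest on it.

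**Conclusion.** The point holds as an unexplained and improvable model choice. Under assumed correlations of -0.3 to -0.5, the expected benefit is a true precision gain of about 0-8% and removal of a possible bias of 0.00-0.06 SD of change. The bias arises only if later missingness depends on baseline; otherwise it is nil. At the higher baseline to follow-up correlations in step 3 (0.9-0.95), the precision gain is smaller still.

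It would go too far to say that the planned LS means are biased, because the documents give neither the dropout pattern nor the correlations. Consequences are limited. The endpoints are secondary, P values are nominal (SAP 10.3.2.3), no between-group comparison is made, and the descriptive tables of raw values and changes do not depend on the model. The change is worth making because it is cheap and makes the missing-at-random assumption more credible. The primary safety objective is untouched.

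**What to change.** In the MMRMs for BMI, BMI-for-age z-score, weight, weight-for-age z-score and absolute and relative ppFEV1:
- Add the previous-study baseline of the analysed variable as a continuous covariate, with its baseline-by-visit interaction.
- Keep both screening strata.
- State the common baseline value at which LS means are evaluated, and that their SEs are conditional on the observed baselines.

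If the sponsor prefers the present models, the SAP should at least give the reason.

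The cost is small. The baselines are already collected, and a subject without one has no change score, so nobody is lost. The interaction needs one slope per modelled visit. For spirometry, weight and height, Study 110 contributes eleven visit windows before follow-up (SAP Appendix D), whose unstructured covariance already needs 11 x 12/2 = 66 parameters. Protocol 12.4.3 leaves these details to the SAP, so no amendment is needed. Two interim analyses have already been run (SAP 11.1). The change should therefore be fixed before the final data lock and justified by the SAP's own practice for its other endpoints, noting that the interaction goes one step beyond that practice.
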